7.3 Treatment Exposure and Compliance

Study drug exposure and compliance will be summarized descriptively by treatment in the safety population.

Study drug compliance will be calculated only for the 24-week main study treatment period and not for the extension period.

7.4 Analysis of Primary Efficacy Endpoint

The primary efficacy endpoint is the mean change from Baseline of proteinuria, as measured by sPCR at Week 24. The sPCR will be \log_{10} -transformed prior to analyses.

7.4.1 Main Analysis

The primary efficacy endpoint will be analyzed using an analysis of covariance (ANCOVA) model based on the ITT population. The ANCOVA model will include both the treatment groups and the presence/absence of endothelial hypercellularity at baseline as factors and adjust for the sPCR at baseline (as a covariate). If required and when possible, missing Week 24 data will be imputed using an appropriate Multiple Imputation (MI) procedure. Should Multiple Imputation procedures fail, last observation carried forward (LOCF) will be used as an alternative imputation algorithm.

The regression method for monotone missing data (SAS PROC MI) will be used for multiple imputation. For patients who discontinued the study due to adverse events, consider the missing data mechanism for the missing change from baseline values to be missing not at random (MNAR). For patients who discontinued the study due to reasons other than adverse events or patients who completed the study but have missing data at a visit, consider the missing data mechanism for the missing change from baseline values to be missing at random (MAR).

Missing data will be imputed in two separate subgroups. The first subgroup will contain all patients randomized to a Fostamatinib group that have data available at the visit or have a MAR missing data mechanism. The second subgroup will contain all patients randomized to placebo as well as fostamatinib patients missing data at the visit with an MNAR missing data mechanism.

Multiple imputation will then be performed within each subgroup, resulting in missing data for Fostamatinib patients under an MAR missing data mechanism imputed from a model obtained only from Fostamatinib treated patients, and missing data from all placebo patients as well as Fostamatinib treated patients with an MNAR missing data mechanism imputed from a model obtained only from placebo treated patients. After obtaining complete data sets for both subgroups, the complete data sets after combining subgroups will be used in the analysis, and inferences from each complete dataset will be combined to obtain an overall test statistic.

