10.3.2 Secondary Efficacy Endpoints

The safety population will include all randomised subjects who received at least 1 dose of the allocated study drug. The safety population will be analyzed for all safety assessments. The subjects will be analyzed as treated.

Secondary efficacy endpoints related to proteinuria will be measured by sPCR (as is the case for the primary efficacy endpoint).

All secondary efficacy endpoints will be analyzed using both the ITT and PP populations. Additionally, the primary efficacy endpoint will be analyzed using the PP population as a sensitivity analysis. No adjustments will be made for multiplicity.

The following secondary endpoints will be analyzed using an ANCOVA model which includes the treatment group and presence/absence of endothelial hypercellularity at baseline as factors, with mean estimates of the variable adjusted for the baseline value:

- Mean change from pre-treatment to post-treatment in mesangial hypercellularity on renal biopsies.
- Mean change from pre-treatment to post-treatment in endocapillary hypercellularity on renal biopsies.
- Mean change from pre-treatment to post-treatment in segmental sclerosis/adhesion on renal biopsies.
- Mean change from pre-treatment to post-treatment in global glomerulosclerosis score on renal biopsies
- Mean change from pre-treatment to post-treatment in tubulointerstitial scarring on renal biopsies.
- Mean change from Baseline (Visit 2) of eGFR at 12 weeks (Visit 7).
- Mean change from Baseline (Visit 2) of eGFR at 24 weeks (Visit 9).
- Mean change from Baseline (Visit 2) of proteinuria at 12 weeks (Visit 7).
- Shift in haematuria (dipstick test) from Baseline (Visit 2) at 12 weeks (Visit 7).

- Shift in haematuria (dipstick test) from Baseline (Visit 2) at 24 weeks (Visit 9).

Estimates will be provided for the following contrasts: 1) combined fostamatinib group vs. placebo; 2); 150 mg fostamatinib group vs. placebo; and 3) 100 mg fostamatinib group vs. placebo.

Fisher's exact test will be used to assess whether the percentage of subjects who meet the following criteria differ between the pooled fostamatinib and placebo groups:

- Have a $\geq 30\%$ reduction in sPCR from Baseline (Visit 2) to Week 24 (Visit 9)
- Have sPCR $< 50\text{mg}/\text{mmoL}$ at Week 12

The 95% CIs for the percentages will also be provided.

Shift tables will display the change in category from Baseline (Visit 2) to Week 24 (Visit 9) for the following categorical parameters:

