7.4.2 Sensitivity Analyses

While the inferential analysis methodology will remain unchanged for sensitivity analyses of the primary endpoint, one method of imputing missing data will be performed before inferential analysis:

The LOCF procedure in the ITT population – This analysis will use an ANCOVA model. The ANCOVA model will include both the treatment group and the presence/absence of endothelial hypercellularity at baseline as factors and adjust for the sPCR at baseline (as a covariate). Dependent variable is change from baseline to Week 24 in sPCR. Missing Week 24 data will be imputed using the LOCF procedure. Pre-treatment values will not be carried forward.

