11.1 Missing Efficacy Data

Missing Week 24 values of sPCR will be imputed using a multiple imputation (MI) procedure for the primary analysis of primary efficacy endpoint and using a last observation carried forward (LOCF) as sensitivity analysis. The details of imputation methods are described in the analysis of efficacy section.

Missing data for the secondary endpoints will not be imputed.

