Step 2a: Impute monotone missing visit using a monotone regression model for non-placebo subjects who discontinued for reasons other than AE

```
proc mi data=OUTMI_1 seed=007 nimpute=1 out=OUTMI_2A;
  where trt01pn>1 & comp24wk^='ADVERSE EVENT';
  class trt01pn endohbl;
  monotone reg(visit9);
  var trt01pn endohbl base visit3--visit9;
run;
```

Step 2b: Impute monotone missing visit using a monotone regression model for placebo subjects or non-placebo subjects who discontinued due AE

```
proc mi data=OUTMI_1 seed=007 nimpute=1 out=OUTMI_2B;
  where trt01pn=1 or (trt01pn>1 & comp24wk='ADVERSE EVENT');
  class endohbl;
  monotone reg(visit9);
  var endohbl base visit3--visit9;
run;
```

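### LOCF is both the fallback for the primary imputation and its only missing-data sensitivity check, so the missing-at-random assumption is never systematically stressed

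*SAP*

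**What the plan says.** **Primary (SAP 7.4.1).** Missing Week 24 sPCR is multiply imputed in two subgroups. For fostamatinib patients who stop for reasons other than an AE, the plan has "missing data for Fostamatinib patients under an MAR missing data mechanism imputed from a model obtained only from Fostamatinib treated patients". For those who stop because of an AE it has "Fostamatinib treated patients with an MNAR missing data mechanism imputed from a model obtained only from placebo treated patients". The example code for the second group (SAP Appendix E, Step 2b) uses "var endohbl base visit3--visit9", so a patient's own on-drug visits are predictors.

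**Fallback (SAP 7.4.1).** "Should Multiple Imputation procedures fail, last observation carried forward (LOCF) will be used as an alternative imputation algorithm". Failure is not defined.

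**Sensitivity (SAP 7.4.2 and 11.1).** Section 7.4.2 says "one method of imputing missing data will be performed before inferential analysis", and that method is LOCF with the same ANCOVA. Section 11.1 repeats the role: "using a last observation carried forward (LOCF) as sensitivity analysis". Section 7.4.2 adds "Pre-treatment values will not be carried forward", so only post-baseline values are carried.

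**Other analyses of the primary endpoint.** Protocol 10.3.2 says "the primary efficacy endpoint will be analyzed using the PP population as a sensitivity analysis", but SAP 5.1 to 5.4 define only ITT, Safety, Biopsy and PK populations. SAP section 6 keeps an analysis with Visit 2 alone as baseline.

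**Protocol on missing data.** Protocol 10.3.1 and 10.8 call for multiple imputation and leave the method to the SAP. The LOCF fallback is a SAP addition.

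**The concern.** A sensitivity analysis should vary the assumption most open to doubt. Here that is MAR for fostamatinib patients who leave for reasons other than an AE, because the primary gives them the drug arm's response to Week 24. No delta, tipping-point or reference-based analysis varies it.

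LOCF changes several things at once. For AE dropouts it removes the placebo-based model and freezes them at a value recorded on drug or at stopping: Protocol 7.9 schedules the withdrawal visit at discontinuation, with the Visit 9 assessments, which include sPCR. For other dropouts it replaces MAR with the last value. Agreement or disagreement between the two analyses therefore cannot be traced to one assumption.

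The fallback adds a second problem. If it is used, the primary gives up its one protective feature and matches its own check. With failure undefined, the switch is discretionary, in a trial where Cohort 1 efficacy is summarised by treatment group before the final analysis (SAP section 8; Protocol 10.9).

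**Working it through.** **The plan's own figure.** SAP 3.2 gives a 43% reduction, CV 0.923, 25 placebo against 50 pooled fostamatinib, and two-sided alpha 0.05.
- Log effect: −ln(0.57) = 0.562. Log SD: √ln(1 + 0.923²) = 0.785.
- SE: 0.785 × √(1/25 + 1/50) = 0.192. Ratio: 0.562/0.192 = 2.92.
- Power is 82.2% (t-test), against a stated 80%. The figure reproduces and is not in dispute.

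**Inputs the documents do not give.** All of the following are assumed: dropout rates, speed of onset (early, linear, late), and within-patient correlation (constant 0.5, 0.7 or 0.85, or autoregressive 0.7). The calculation takes the pooled contrast and omits the stratum.

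**Formula.** Let a be the share of fostamatinib patients who are AE dropouts and m the share who are other dropouts. Let r be the share of the full drug effect credited to a dropout at Week 24.
- Primary: 0.562 × [1 − a(1 − r_P)]. MAR credits other dropouts with the full effect, so m drops out.
- LOCF: 0.562 × [1 − (a + m)(1 − r_L)].
- Reduction = 1 − exp(−log effect).

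For AE dropouts r_L ran from 0.28 to 0.96 and r_P from 0.07 to 0.63. The primary does not set r_P to zero, because Step 2b conditions on on-drug visits. LOCF was the more favourable for AE dropouts in every setting.

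**Three settings, true 43% reduction, constant correlation 0.5**

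| Onset | a | m | r_L | r_P | LOCF | Primary |
|---|---|---|---|---|---|---|
| Early | 10% | 0 | 0.96 | about 0.5 | 42.9% | 41.4% |
| Linear | 10% | 5% | 0.37 | 0.12 | 39.9% | 40.1% |
| Late | 10% | 10% | 0.28 | 0.07 | 38.2% | 39.9% |

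The early r_P is solved back from 41.4%. The last row in full:
- LOCF: 0.562 × (1 − 0.20 × 0.72) = 0.481, giving 38.2%.
- Primary: 0.562 × (1 − 0.10 × 0.93) = 0.510, giving 39.9%.

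**Where the order turns.** LOCF gives the smaller effect when m(1 − r_L) > a(r_L − r_P).
- Linear: m/a above 0.25/0.63 = 0.40.
- Late: m/a above 0.21/0.72 = 0.29.
- Early: m/a above about 0.45/0.04 = 11, which is out of practical reach.

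Three onset shapes, four correlations and four dropout mixes (AE and other: 10% and 0, 10% and 5%, 10% and 10%, 20% and 5%) make 48 settings. LOCF was less conservative in 30 and more conservative in 18. With AE dropout only (10%) it gave the larger effect in all 12.

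**Rejection rates.** The simulation used 1,000 trials per setting in the rows quoted with three decimals, 25 against 50 patients, and 10 imputations combined by Rubin's rules against a single LOCF ANCOVA.
- Early onset, correlation 0.5, true 30%, 20% AE and 5% other dropout: LOCF 0.56, primary 0.34. Mean estimates were 30.0% and 27.9%.
- Late onset, correlation 0.5, true 43%, 5% AE and 15% other dropout: LOCF 0.807, primary 0.815.
- No drug effect (early setting, correlation 0.7, 10% AE and 5% other dropout): LOCF 0.047, primary 0.027.

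Most of the gap between 0.56 and 0.34 is precision. A rate of 0.56 implies an SE near 0.357/(1.96 + 0.15) = 0.169. At that SE, the primary's log effect of 0.327 would reject about 0.49 of the time. The fall from 0.49 to 0.34 comes from the wider SE that multiple imputation carries and single LOCF does not.

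**The case against.** **LOCF is a real alternative.** It replaces the MAR imputation of non-AE dropouts with their own last value and can move the result either way. A reader might infer that LOCF cannot test the primary at all. That goes too far: it is an unsystematic check, but it is a check.

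**LOCF is not always the lenient method.** A reader might also infer that LOCF is less conservative than the primary in general. The documents do not support that. It holds for AE dropouts when the drug works, but 18 of the 48 settings go the other way overall. It would also fail for an AE dropout whose last sPCR was worse than the placebo prediction. Nor did LOCF inflate the false-positive rate in the no-effect setting simulated.

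**Other analyses remain.** The Visit 2-only baseline analysis is kept, and the Week 24 responder endpoints are analysed without imputation. So LOCF is the only missing-data sensitivity analysis in the SAP, not the only second look. But the Visit 2-only analysis leaves the missing-data assumption unchanged, and the responder analyses are observed-data looks at other endpoints. A per-protocol analysis would not test that assumption either; its absence from the SAP is a separate discrepancy.

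**The fallback is contingent.** Example code is supplied, and nothing shows that failure is likely. That lowers the urgency, but an undefined trigger is still an open choice of primary method.

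**Conclusion.** The point holds in this form. LOCF is both fallback and sole missing-data sensitivity analysis. It favours fostamatinib AE dropouts relative to the placebo-based primary when the drug works, and nothing systematically varies MAR for the other dropouts. If the fallback is used, the primary loses its placebo-based handling and coincides with its sensitivity analysis, assuming both treat pre-treatment values alike; 7.4.1 is silent on that.

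The modelled differences in the estimate are small, from 1.5 points in LOCF's favour to 1.7 points against it in the tabulated settings. The difference in rejection rate can be large (0.56 against 0.34), so the choice of method could decide significance. All of these sizes rest on assumed dropout, onset and correlation. For a proof-of-concept trial this is a change worth making, not a flaw that invalidates the primary analysis.

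**What to change.** **SAP 7.4.2 and 11.1.** Make the main sensitivity analysis one of these:
- placebo-based imputation for all fostamatinib dropouts, by changing the WHERE clauses in Steps 2a and 2b of Appendix E so that every fostamatinib discontinuation moves to the Step 2b group; or
- a delta or tipping-point analysis on the non-AE dropouts, leaving the AE handling as it is.

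Keep LOCF as supplementary only.

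**SAP 7.4.1.** State what counts as imputation failure. Replace the LOCF fallback with one that keeps placebo-based handling of AE dropouts, for example a simpler imputation model with fewer visits as predictors. A likelihood-based repeated-measures model that treats AE dropouts as MAR is not a suitable substitute, because it drops the same protection.

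**Cost.** SAP wording and modest programming, with no new data. The sensitivity estimate may be less favourable to the drug.

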7.4.2 Sensitivity Analyses

While the inferential analysis methodology will remain unchanged for sensitivity analyses of the primary endpoint, one method of imputing missing data will be performed before inferential analysis:

The LOCF procedure in the ITT population – This analysis will use an ANCOVA model. The ANCOVA model will include both the treatment group and the presence/absence of endothelial hypercellularity at baseline as factors and adjust for the sPCR at baseline (as a covariate). Dependent variable is change from baseline to Week 24 in sPCR. Missing Week 24 data will be imputed using the LOCF procedure. Pre-treatment values will not be carried forward.

7.4.3 Subgroup Analysis

Sample size permitting, the primary efficacy analysis will also be conducted for the following subgroups:

1. Time since initial exposure to RAS blockade (< 6 months vs ≥ 6 months from baseline). The initial exposure to RAS blockade (angiotensin II receptor blocker (ARB) or angiotensin converting enzyme inhibitor (ACEI)) will be derived from prior/concomitant medication collected on CRF. The imputed medication start date will be used to calculate the duration of the exposure from baseline.
2. Baseline sPCR: sPCR > 2000 mg/g and sPCR > 3500 mg/g.

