3.2 Determination of Sample Size

A sample size of 25 evaluable subjects in each of the 3 treatment groups will have an 80% power to detect a 43% reduction in sPCR from Baseline to Week 24 between the pooled fostamatinib and placebo groups, using a 2-sided t-test with $\alpha = 0.05$ and log-transformed data. This calculation assumes that the 3 treatment groups have the same mean and standard deviations of urinary protein/creatinine ratio and coefficient of variation of 0.923 at Baseline and that the values for the placebo group remain constant over 24 weeks. Treatment allocation ratio will be 1:2 for the placebo: combined fostamatinib groups

Table 1 Study Treatment

Treatment Group	Number of Subjects	Dose
C	25	Placebo bid
A	25	Fostamatinib 100 mg bid
B	25	Fostamatinib 150 mg bid

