5.5 Treatment Groups for Analysis

For descriptive summaries, the following treatment groups will be used, unless otherwise indicated.

- Placebo (all placebo groups)
- 100 mg bid fostamatinib group
- 150 mg bid fostamatinib group
- Combined fostamatinib group

For comparisons of treatment differences in the analyses of efficacy endpoints, estimates of the following contrasts will be provided, unless otherwise indicated:

- Combined fostamatinib group vs placebo
- 150 mg bid fostamatinib group vs placebo
- 100 mg bid fostamatinib group vs placebo

For all the by-subject listings, the randomized treatment group will be presented.

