5.8 Multiplicity Considerations

No adjustments for multiplicity will be applied

6. Analytic Definitions

Age at Baseline is the last non-missing age collected before the first dose of study treatment.

Body Mass Index is calculated as $(\text{Weight in kg}/(\text{Height in meter})^2)$. The last non-missing weight and height collected before the first dose of study treatment will be used to calculate the baseline BMI.

Baseline Measurements will be the last measurement for the corresponding variable prior to the first randomized dose at Visit 2. For analysis of the primary efficacy endpoint, the main analysis will be performed with baseline defined as the average between Visit 2 and the most recent screening value prior to Visit 2 (a secondary analysis, with the Visit 2 value alone as baseline, will be performed).

Study Day will be the number of days from first dose date of study drug for the assessments prior to the first dose date to assessment date. That is:

$$\text{Study Day of post-dose assessment} = \text{Assessment Date} - \text{First Dose Date} + 1.$$

$$\text{Study Day of pre-dose assessment} = \text{Assessment Date} - \text{First Dose Date}$$

Pre-treatment assessments could be up to 180 days prior to baseline. If there are more than two pre-treatment assessments for a subject, the last assessments will be used for the analyses related to 'pre-treatment'. Post-treatment assessments will be the assessments after the first dose of study drug. If there are more than two post-treatment assessments for a subject within an analysis visit, the last assessment that is closest to the scheduled study day will be used for the analyses related to 'post-treatment'.

Study Drug Exposure is calculated as number of days from first dose day to last. That is:

$$\text{Study Drug Exposure} = \text{Last Study Drug Date} - \text{First Study Drug Date} + 1.$$

Study Drug Compliance (%) for a subject is calculated as: $100 * (\text{total number of tablets dispensed during the double-blind treatment period} - \text{total number of tablets returned during the double-blind treatment period}) / \text{total number of tablets the subject was supposed to taken during the double-blind treatment period per protocol}$:

$$\text{Compliance (\%)} = 100 \times (\sum_{i=1}^6 D_i - \sum_{i=1}^6 R_i) / \sum_{i=1}^6 T_i * P_i$$

where:

i = study drug dispensation/return visit interval, $i = 1$ to 6

D_i = total number of tablets dispensed for visit interval i

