R_i = total number of tablets returned for visit interval i

$T_i = 2$ for bid dosing and $=1$ for qd dosing, for visit interval i

P_i = total number of days in visit interval i .

The total number of tablets that were supposed to be taken during the double-blind treatment period excludes the number of tablets not taken due to a dose interruption. If a patient fails to return a study drug kit dispensed during the double-blind treatment period, then study drug compliance is considered to be missing.

Baseline sPCR: Two baseline sPCR value will be used in the analysis. In primary efficacy analysis, the baseline sPCR is defined as the average of non-missing value between Visit 2 and the most recent screening value prior to Visit 2. If only one non-missing sPCR is available, this value will be used as baseline.

A **Treatment-Emergent Adverse Event (TEAE)** is any adverse event that emerges on or after first dosing and prior to the end of follow-up (having been absent prior to treatment) or worsens relative to the pre-treatment state.

Hy's Law criteria are: concurrent aspartate aminotransferase (AST) or alanine aminotransferase (ALT) $\geq 3x$ upper limit of normal (ULN) with total (and/or direct/conjugated) bilirubin (TBL) $> 2x$ ULN and alkaline phosphatase (ALP) $< 2x$ ULN, and no other reason can be found to explain the combination of increased aminotransferase and serum total bilirubin, such as viral hepatitis, alcohol abuse, ischemia, preexisting liver disease, or another drug capable of causing the observed injury.

Prior Medications will be defined as the medications used prior to the first dose of study drug. If the medication is used both prior to and on/after the first dose of study drug, the medication is both prior medication and concomitant medication.

Concomitant Medication will be defined as the medications used on/after the first dose of study drug.

7. Statistical Methods

The statistical analysis of the data obtained from this study will be performed using SAS® version 9.4 or higher. All inferential tests will be 2-sided and will be performed using a type I error rate of 5%, unless otherwise indicated.

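### SAP 7.4.3 repeats the primary test separately in the two RAS-blockade-duration groups but never compares them; add a treatment-by-duration estimate and label the analysis exploratory.

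*SAP*

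**What the plan says.** SAP 7.4.3 reads: "Sample size permitting, the primary efficacy analysis will also be conducted for the following subgroups". Item 1 is "Time since initial exposure to RAS blockade (< 6 months vs ≥ 6 months from baseline"). No threshold for a sufficient sample is stated.

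The analysis to be repeated is the ANCOVA of SAP 7.4.1. It has main effects only: treatment group, hypercellularity stratum and baseline sPCR. Neither document contains an interaction term or an interaction test.

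Three general rules carry over to the subgroups because 7.4.3 does not switch them off:

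- The opening of SAP Section 7: "All inferential tests will be 2-sided and will be performed using a type I error rate of 5%, unless otherwise indicated".
- SAP 5.8: "No adjustments for multiplicity will be applied".
- SAP 5.5: "For comparisons of treatment differences in the analyses of efficacy endpoints, estimates of the following contrasts will be provided, unless otherwise indicated". The three contrasts are pooled fostamatinib, 150 mg and 100 mg, each against placebo.

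Elsewhere the SAP limits an analysis when it means to. The immunohistochemistry endpoints are headed exploratory (4.6), safety has no inferential statistics (7.6), and interim efficacy is descriptive only (Section 8). Section 7.4.3 has no such limit. The protocol plans no subgroup analysis, but its Section 10.1 leaves detail to the SAP, so this is not a conflict.

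**The concern.** Item 1 sets short against long RAS blockade, so its question is whether the drug effect differs between the two. The planned output does not answer that question. It gives two separate results from parts of a trial sized for one comparison in the whole. When each part has modest power, the same true effect in everyone will often reach p < 0.05 in one group and miss it in the other.

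In a proof-of-concept study, a false impression that the drug works only in one group could steer the choice of population for the next trial. If there is no effect at all, separate tests also give extra chances of a nominally significant result on the primary variable.

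The SAP already recognises the power problem in two similar settings. Section 7.4.4 drops regional analysis because the sample is small. Section 8 says power midway through the trial, with a first cohort of 38 (SAP 3.1), is too low for decisions on efficacy. An even RAS split would give groups of about that size.

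**Working it through.** **Inputs (SAP 3.2).** "A sample size of 25 evaluable subjects in each of the 3 treatment groups"; power 80% for a 43% fall in sPCR, pooled fostamatinib against placebo; CV 0.923; two-sided 5%; log-transformed data; placebo constant; 1:2 allocation. The protocol's 130 ± 120 mg/mmol gives the same CV (120/130 = 0.923). The share of subjects in each RAS group is not given, so it is assumed and varied.

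**Reproducing the plan's figure.**
- Log SD = √ln(1 + 0.923²) = 0.785.
- Effect = −ln(1 − 0.43) = −ln 0.57 = 0.562.
- SE = 0.785 × √(1/25 + 1/50) = 0.192. The noncentral-t power at 25 vs 50 is 82.2%, and 24 placebo subjects already give 80.6%.
- The stated 25 per group therefore reproduces, slightly on the conservative side.

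**Same 43% effect in both groups, pooled contrast.** With a share f in the smaller group, that group has 25f placebo and 50f fostamatinib subjects. Let p1 and p2 be the power in the two groups. Then P(significant in exactly one) = p1(1 − p2) + p2(1 − p1).

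| Assumed split | p1 | p2 | Exactly one significant |
|---|---|---|---|
| 50/50 | 0.520 | 0.520 | 50% |
| 33/67 | 0.366 | 0.648 | 54% |
| 20/80 | 0.228 | 0.729 | 62% |
| 10/90 | 0.121 | 0.780 | 71% |

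For the even split: 2 × 0.520 × 0.480 = 0.499. Both groups are significant in 27% of trials and neither in 23%. A simulation of 100,000 trials gave 50.1%.

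**How far the figure moves.**
- Other uniform effects, even split: no effect 9.5%; 20% reduction 22%; 30% reduction 37%; 50% reduction 42%; 60% reduction 17%.
- Baseline adjustment, which shrinks the SD to 0.785 × √(1 − ρ²) for an assumed baseline-to-Week 24 log correlation ρ of 0.5, 0.6 or 0.7: even split 46%, 41%, 32%; 20/80 split 65%, 64%, 60%.

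**Interaction test instead.** At the uniform design effect it rejects in 4.95% of simulated trials (even split) and 4.99% (25/75). Its precision is poor:
- Even split: SE in each group = 0.785 × √(1/12.5 + 1/25) = 0.272; SE of the difference = 0.272 × √2 = 0.385.
- Power for a 43% effect in one half and none in the other: 0.562/0.385 = 1.46, and P(Z > 1.96 − 1.46) is about 31%.
- 95% CI half-width = 1.96 × 0.385 = 0.754, a factor of about 2.1 either way on the ratio of effects.

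**No drug effect.** Pooled contrast in two separate groups: 1 − 0.95² = 9.75%. If all three contrasts are tested in each group (six tests), simulation at even, 33/67 and 20/80 splits gives 17% to 19%.

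**The case against.** Several parts of the case for leaving 7.4.3 alone stand.

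- **The split is unknown.** A reader might infer that a uniform effect will look subgroup-specific half the time. The documents do not support that: they never say the groups are halves. Protocol 6.1 requires at least 90 days of ACEi or ARB before Visit 1b, which confines the short group to roughly 3 to 6 months of exposure, so an uneven split is plausible. With an even split, 2p(1 − p) cannot exceed 50%, so that figure is a ceiling.
- **The planned model adjusts for baseline.** The design figures do not. Strong adjustment lowers the even-split figure to about 32% at ρ = 0.7, though hardly at all for a 20/80 split.
- **The analysis may not be run.** The opening condition could stop it, most likely when one group is very small. But no threshold is stated, and the condition does not change the method if the analysis goes ahead.
- **Estimates are promised.** A reader might infer that the output can be read only as significant in one group and not in the other. SAP 5.5 provides estimates of contrasts, which can be set side by side, and no decision rule is attached to the subgroup p-values. The 50% is therefore how often a misleading pattern would appear, not the error rate of a planned decision. It differs in kind from the interaction test's 5%, which is its alpha by construction.
- **No efficacy claim rests on 7.4.3.** A reader might infer that the trial's primary error rate rises to 17% or more. It does not: SAP 5.1 gives primary status to the ITT analyses, and the absence of multiplicity adjustment is declared openly. Much of the 17% to 19% comes from the by-dose contrasts; the subgroup split alone accounts for about 10%. Counting six tests is itself a reading of SAP 5.5.

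None of this supplies the missing comparison between the two groups, or the missing label.

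**Conclusion.** The point holds as a cheap improvement. SAP 7.4.3 item 1 asks whether RAS-blockade duration matters, repeats the primary ANCOVA in each group, and plans no estimate of the difference between groups and no exploratory label.

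The 50% (even split) and 54% to 62% (33/67 to 20/80) figures rest on the SAP's design effect and variability, the same effect in both groups, no baseline adjustment, and splits that are assumed. Relaxing these gives a range of about 10% to 70%. Apart from very small or very large effects, the figure stays several times the 5% of an interaction test. The primary ITT analysis is untouched.

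**What to change.** In SAP 7.4.3 item 1, replace the separate analyses with one ANCOVA in the full ITT set: log sPCR change on treatment, endocapillary stratum, baseline log sPCR, RAS-duration group and treatment × RAS-duration. Report the interaction as a ratio of effects with its 95% CI, and each group's effect with a 95% CI from the same model, in place of separate within-group p-values. State that the subgroup analysis is exploratory and is not a basis for an efficacy claim.

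The cost is one subgroup main effect, its interaction with treatment and a sentence or two of text, with no new data. The example imputation code in SAP Appendix E does not include RAS duration, so the SAP should say whether the imputation model needs it for this analysis.

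The downside is imprecision. With about 31% power even for an effect confined to one half, the interval will be wide, and the SAP should say that a non-significant interaction does not show that the effect is uniform.
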